8.1.3 Adverse events of special interest

See [Section 6.3.1.1](#) through [Section 6.3.1.7](#).

8.2 Serious adverse events

8.2.1 Definitions

Serious adverse event (SAE) is defined as one of the following:

- Is fatal or life-threatening
- Results in persistent or significant disability/incapacity
- Constitutes a congenital anomaly/birth defect
- Is medically significant, i.e., defined as an event that jeopardizes the patient or may require medical or surgical intervention to prevent one of the outcomes listed above
- Requires inpatient hospitalization or prolongation of existing hospitalization,
- Note that hospitalizations for the following reasons should not be reported as serious adverse events:
 - Routine treatment or monitoring of the studied indication, not associated with any deterioration in condition
 - Elective or pre-planned treatment for a pre-existing condition that is unrelated to the indication under study and has not worsened since signing the informed consent
 - Social reasons and respite care in the absence of any deterioration in the patient's general condition
- Note that treatment on an emergency outpatient basis that does not result in hospital admission and involves an event not fulfilling any of the definitions of a SAE given above is not a serious adverse event

8.2.2 Reporting

To ensure patient safety, every SAE, regardless of suspected causality, occurring after the patient has provided informed consent and until at least 30 days after the patient has stopped study treatment must be reported to Novartis within 24 hours of learning of its occurrence.

Any SAEs experienced after this 30 days period should only be reported to Novartis if the investigator suspects a causal relationship to the study treatment. Recurrent episodes, complications, or progression of the initial SAE must be reported as follow-up to the original episode within 24 hours of the investigator receiving the follow-up information. An SAE occurring at a different time interval or otherwise considered completely unrelated to a previously reported one should be reported separately as a new event.

Information about all SAEs is collected and recorded on the Serious Adverse Event Report Form; all applicable sections of the form must be completed in order to provide a clinically thorough report. The investigator must assess and record the relationship of each SAE to each specific study treatment (if there is more than one study treatment), complete the SAE Report Form in English, and send the completed, signed form by fax within 24 hours to the oncology Novartis Drug Safety and Epidemiology (DS&E) department.

The telephone and telefax number of the contact persons in the local department of Drug Safety and Epidemiology (DS&E), specific to the site, are listed in the investigator folder

provided to each site. The original copy of the SAE Report Form and the fax confirmation sheet must be kept with the case report form documentation at the study site.

Follow-up information is sent to the same contact(s) to which the original SAE Report Form was sent, using a new SAE Report Form stating that this is a follow-up to the previously reported SAE and giving the date of the original report. Each re-occurrence, complication, or progression of the original event should be reported as a follow-up to that event regardless of when it occurs. The follow-up information should describe whether the event has resolved or continues, if and how it was treated, whether the blind was broken or not, and whether the patient continued or withdrew from study participation.

If the SAE is not previously documented in the [Investigator's Brochure] or Package Insert (new occurrence) and is thought to be related to the Novartis study treatment, an oncology Novartis Drug Safety and Epidemiology (DS&E) department associate may urgently require further information from the investigator for Health Authority reporting. Novartis may need to issue an Investigator Notification (IN), to inform all investigators involved in any study with the same drug that this SAE has been reported. Suspected Unexpected Serious Adverse Reactions (SUSARs) will be collected and reported to the competent authorities and relevant ethics committees in accordance with Directive 2001/20/EC or as per national regulatory requirements in participating countries.

8.3 Emergency unblinding of treatment assignment

Not applicable, this is an open-label treatment study.

8.4 Pregnancies

To ensure patient safety, each pregnancy occurring while the patient is on study treatment must be reported to Novartis within 24 hours of learning of its occurrence. The pregnancy should be followed up to determine outcome, including spontaneous or voluntary termination, details of the birth, and the presence or absence of any birth defects, congenital abnormalities, or maternal and/or newborn complications.

[figure not shown]
Pregnancy should be recorded on a Clinical Trial Pregnancy Form and reported by the investigator to the oncology Novartis Drug Safety and Epidemiology Department (DS&E). Pregnancy follow-up should be recorded on the same form and should include an assessment of the possible relationship to the study treatment any pregnancy outcome. Any SAE experienced during pregnancy must be reported on the SAE Report Form.

8.5 Warnings and precautions

No evidence available at the time of the approval of this study protocol indicated that special warnings or precautions were appropriate, other than those noted in the provided Investigator Brochure. Additional safety information collected between IB updates will be communicated in the form of Investigator Notifications. This information will be included in the patient informed consent and should be discussed with the patient during the study as needed.

8.6 Data Monitoring Committee

Not applicable.

8.7 Steering Committee

Not applicable.

9 Data collection and management

9.1 Data confidentiality

Information about study subjects will be kept confidential and managed under the applicable laws and regulations. Those regulations require a signed subject authorization informing the subject of the following:

- What protected health information (PHI) will be collected from subjects in this study
- Who will have access to that information and why
- Who will use or disclose that information
- The rights of a research subject to revoke their authorization for use of their PHI.

In the event that a subject revokes authorization to collect or use PHI, the investigator, by regulation, retains the ability to use all information collected prior to the revocation of subject authorization. For subjects that have revoked authorization to collect or use PHI, attempts should be made to obtain permission to collect follow-up safety information (e.g. has the subject experienced any new or worsened AEs) at the end of their scheduled study period.

The data collection system for this study uses built-in security features to encrypt all data for transmission in both directions, preventing unauthorized access to confidential participant information. Access to the system will be controlled by a sequence of individually assigned user identification codes and passwords, made available only to authorized personnel who have completed prerequisite training.

9.2 Site monitoring

Before study initiation, at a site initiation visit or at an investigator's meeting, Novartis personnel (or designated CRO) will review the protocol and CRFs with the investigators and their staff. During the study, the field monitor will visit the site regularly to check the completeness of patient records, the accuracy of entries on the CRFs, the adherence to the protocol to Good Clinical Practice, the progress of enrollment, and to ensure that study treatment is being stored, dispensed, and accounted for according to specifications. Key study personnel must be available to assist the field monitor during these visits.

The investigator must maintain source documents for each patient in the study, consisting of case and visit notes (hospital or clinic medical records) containing demographic and medical information, laboratory data, electrocardiograms, and the results of any other tests or assessments. All information recorded on CRFs must be traceable to source documents in the patient's file. The investigator must also keep the original signed informed consent form (a signed copy is given to the patient).

The investigator must give the monitor access to all relevant source documents to confirm their consistency with the CRF entries. Novartis monitoring standards require full verification for the presence of informed consent, adherence to the inclusion/exclusion criteria and

documentation of SAEs. Additional checks of the consistency of the source data with the CRFs are performed according to the study-specific monitoring plan.

9.3 Data collection

For studies using Electronic Data Capture (EDC), the designated investigator staff will enter the data required by the protocol into the Electronic Case Report Forms (eCRF). The eCRFs have been built using fully validated secure web-enabled software that conforms to 21 CFR Part 11 requirements, Investigator site staff will not be given access to the EDC system until they have been trained. Automatic validation programs check for data discrepancies in the eCRFs and, allow modification or verification of the entered data by the investigator staff.

The Principal Investigator is responsible for assuring that the data entered into eCRF is complete, accurate, and that entry and updates are performed in a timely manner.

9.4 Database management and quality control

For studies using eCRFs, Novartis personnel (or designated CRO) will review the data entered by investigational staff for completeness and accuracy. Electronic data queries stating the nature of the problem and requesting clarification will be created for discrepancies and missing values and sent to the investigational site via the EDC system. Designated investigator site staff are required to respond promptly to queries and to make any necessary changes to the data.

[figure not shown]
Concomitant treatments and prior medications entered into the database will be coded using the WHO Drug Reference List, which employs the Anatomical Therapeutic Chemical classification system. Medical history/current medical conditions and adverse events will be coded using the Medical dictionary for regulatory activities (MedDRA) terminology.

Samples and/or data will be processed centrally and the results will be sent electronically to Novartis (or a designated CRO).

Randomization codes and data about all study treatments dispensed to the patient will be tracked using an Interactive Response Technology. The system will be supplied by a vendor(s), who will also manage the database. The data will be sent electronically to Novartis personnel (or designated CRO).

At the conclusion of the study, the occurrence of any emergency code breaks will be determined after return of all code break reports and unused drug supplies to Novartis personnel (or designated CRO). The occurrence of any protocol violations will be determined. After these actions have been completed and the data has been verified to be complete and accurate, the database will be declared locked. Authorization is required prior to making any database changes to locked data, by joint written agreement between the Global Head of Biostatistics and Data Management and the Global Head of Clinical Development.

For EDC studies, after database lock, the investigator will receive a CD-ROM or paper copies of the patient data for archiving at the investigational site.

10 Statistical methods and data analysis

This is an open-label, phase II, randomized, pilot study to assess the efficacy in term of erythroid improvement of DFX combined with EPO compared to EPO alone in patients with low- or int-1-risk myelodysplastic syndrome.

The data will be analyzed by Novartis and/or a designated CRO.

Continuous variables will be summarized by number of patients, mean, standard deviation, minimum, 25th-percentile, median, 75th percentile and maximum. Categorical variables will be summarized by absolute and relative frequencies.

In addition to the statistical methods outlined below, further details and any additional, exploratory analyses that may be performed will be described in the Report and Analysis Plan (RAP).

10.1 Analysis sets

10.1.1 Full Analysis Set

The Full Analysis Set (FAS) comprises all patients to whom study treatment has been assigned by randomization (EPO or EPO+DFX). According to the intent to treat principle, patients will be analyzed according to the treatment they have been assigned to during the randomization procedure.

10.1.2 Safety Set

The Safety Set includes all randomized patients who received at least one dose of study medication, i.e. either EPO or EPO+DFX, and with at least one post-baseline safety assessment (e.g. lab, vital signs, AEs) and the statement that a subject did not experience an AE can currently be regarded as a valid safety assessment.

[figure not shown]
10.1.3 Per Protocol Set

The per protocol (PP) set consists of all patients from the Full Analysis Set without any major protocol deviation, who have been randomized, are evaluable for efficacy (has both baseline and at least one post-baseline value for Hb) and who received at least one dose of assigned study medication.

However, if a patient discontinued for adverse event or died before the minimum exposure requirement could be met, or before he/she could become evaluable for efficacy, the patient will still be included in the PP set.

10.2 Patient demographics/other baseline characteristics

Demographic and other baseline data and disease characteristics will be summarized descriptively by treatment group for the FAS.

10.3 Treatments (study treatment, concomitant therapies, compliance)

Duration of study drug exposure for EPO and DFX as well as DFX planned dose (mg/kg/day), DFX actual dose (mg/day) and EPO planned and actual dose (units/week) will be summarized. Frequency tables for dose adjustments and related reason will be provided for DFX and EPO by treatment group as well as number of dose interruptions. Any dose adjustments and reasons will be listed.

Descriptive statistics will be provided for frequency of patients switching at 12 weeks to other treatment regimen, as per EPO guidelines.

DFX compliance based on prescribed amount of study medication versus amount of medication taken based on dispensed and returned amount of study medication will be summarized.

Concomitant medications and significant non-drug therapies prior to and after the start of the study treatment will also be provided. Analysis will be done on safety set.

10.4 Primary objective

The primary objective is to assess the effect of treatment with DFX combined with EPO vs. EPO alone on erythropoiesis.

10.4.1 Variable

The primary variable is the difference in proportion of patients achieving an erythroid response after 12 weeks of treatment between the two arms according to a criterion based on modified IWG 2006 (increase in Hb from baseline ≥ 1.5 g/dL).

Patients meeting the criterion at any time within the first 12 weeks period will be considered as erythroid responders.

10.4.2 Statistical hypothesis, model, and method of analysis

[figure not shown]
A patient is defined as an erythroid responder if the criterion of Hb increase from baseline ≥ 1.5 g/dL is met at any time within the first 12 weeks period. Baseline is defined as the last available Hb value available within windows of 4 weeks prior to or on treatment start date. No imputation will be performed for missing laboratory data.

Difference in proportions between treatment groups with its 95% Agresti-Caffo ([Agresti-Caffo 2000](#)) confidence interval will be provided. Erythroid response proportion will be also summarized by treatment group with its 95% Clopper-Pearson confidence intervals. Analysis will be performed on FAS and PP set.

10.5 Secondary objectives

10.5.1 To assess the effect of treatment with DFX+EPO and EPO alone on hematological response within 24 weeks of treatment

This analysis includes patients who were randomized to EPO and EPO+DFX and remained in their respective treatment arms.

Hematological response will be assessed on this subset of patients and hematological responder is defined as patient meeting at least one of the following modified IWG 2006 criteria:

Hematological response:

- Hb increase from baseline ≥ 1.5 g/dL and Hb < 11 g/dL at baseline (All patients on study per inclusion criterion 5, section 5.2)
- Neutrophil response: Neutrophil increase from baseline of $\geq 100\%$ and increase $> 0.5 \times 10^9/L$ and neutrophils $< 1.0 \times 10^9/L$ at baseline
- Platelet response: Platelet increase from baseline of $\geq 30 \times 10^9/L$ and platelets $< 100 \times 10^9/L$ at baseline

[figure not shown]
Patients who met at least one of the 3 conditions of hematological response at any time between first day of treatment and week 24 will be considered as responders.

Supportive analyses (proportion of patients, descriptive statistics on the related parameters, change from baseline) will also be provided for patients who do not satisfy the IWG 2006 pre-treatment conditions for neutrophil and/or platelet response (i.e., these patients have baseline neutrophils $\geq 1.0 \times 10^9/L$ and baseline platelets $\geq 100 \times 10^9/L$) but show hematologic improvement with respect to neutrophils (increase from baseline $> 0.5 \times 10^9/L$) and platelets (increase from baseline $\geq 30 \times 10^9/L$).

Proportion of patients achieving a hematological response within 24 weeks of treatment with DFX combined with EPO and EPO alone will be calculated along with 95% Clopper-Pearson confidence interval. Descriptive statistics will be provided for hematological response, as well as for all improvement of myeloid cell lineages (erythrocytes, neutrophils and platelets). Analysis will be performed on FAS and PP set.

Table 10-1 Criteria for hematological response and hematologic improvement

	Pre-treatment conditions	Post-baseline	Response
Hematological response: If a patient fulfills at least erythroid or platelet or neutrophil response as well as it's corresponding pre-treatment condition	Hb < 11 g/dL at baseline Platelet $< 100 \times 10^9/L$ at baseline Neutrophil $< 1.0 \times 10^9/L$ at baseline	Hb increase from baseline by ≥ 1.5 g/dL Increase from baseline $\geq 30 \times 10^9/L$ Increase from baseline $> 100\%$ and increase from baseline $> 0.5 \times 10^9/L$	Erythroid response Platelet response Neutrophil response
Hematologic improvement: If a patient fulfills at least platelet or neutrophil improvement response without it's corresponding pre-treatment condition	Platelet $\geq 100 \times 10^9/L$ at baseline Neutrophil $\geq 1.0 \times 10^9/L$ at baseline	Increase from baseline $\geq 30 \times 10^9/L$ Increase from baseline $> 0.5 \times 10^9/L$	Platelet improvement Neutrophil improvement

10.5.2 To assess the effect of treatment on erythropoiesis within 24 weeks in patients who were non-responder to EPO alone after 12 weeks and switched to DFX+EPO

Patients who are non-responders to erythroid at week 12 in the EPO group will have to switch to combination therapy, if they continue to participate in the study.

Patients meeting the criterion (Hb increase from baseline ≥ 1.5 g/dL) at any time between week 12 and week 24 will be considered as erythroid responders.

Proportion of erythroid responders between week 13 and 24 will be reported along with its 95% Clopper-Pearson confidence interval. Descriptive statistics will be provided for erythroid response. Analysis will be performed on FAS and PP set.

10.5.3 To assess time to erythroid response in patients treated with DFX+EPO and patients treated with EPO alone

This analysis will include patients who were randomized to EPO and EPO+DFX and remained in their respective treatment arms. Descriptive statistics will be provided for erythroid responder patients (achieved Hb increase ≥ 1.5 g/dL from baseline) for time to response (days), defined as the time from date of start of treatment to the date of event defined as the first documented erythroid response between week 1 to week 24. Analysis will be performed on FAS and PP set for both treatment groups.

10.5.4 To assess the effect of treatment with EPO alone on erythropoiesis after 24 weeks of treatment

[figure not shown]
This analysis includes patients who started with the EPO alone and are not switched to combination therapy.

Patients meeting the criterion (Hb increase from baseline ≥ 1.5 g/dL) at any time between week 1 and week 24 will be considered as erythroid responders.

Proportion of erythroid responders who starts with EPO alone and are not switched to combination therapy will be reported along with its 95% Clopper-Pearson confidence interval. Descriptive statistics will be provided for erythroid response. Analysis will be performed on FAS and PP set.

10.5.5 To estimate time to erythroid response in patients who were non-responder to EPO alone after 12 weeks and switched to DFX+EPO

Descriptive statistics will be provided for erythroid responder patients (achieved Hb increase ≥ 1.5 g/dL from baseline) for time to response (days), defined as the time from date of switch to combination to the date of event defined as the first documented erythroid response within the period between week 13 and week 24. Analysis will be performed on FAS and PP set.

10.5.6 To estimate time to hematological response in patients treated with DFX+EPO and EPO alone within 24 weeks

This analysis includes patients who started with combination therapy and EPO alone and remained in their respective treatment arms.

Descriptive statistics will be provided for responder patients for time to response (days), defined as the time from date of start of treatment to the date of event defined as the first documented hematological response (increase in Hb, improvement of neutropenia and thrombocytopenia) up to week 24.

Hematological response will be assessed on this subset of patients and hematological response is defined for patients meeting at least one of the following modified IWG 2006 criteria:

- Hb increase from baseline ≥ 1.5 g/dL and Hb < 11 g/dL at baseline (all patients on study per inclusion criterion 5, [Section 5.2](#)).
- Neutrophil response: increase from baseline of $\geq 100\%$ and increase $> 0.5 \times 10^9/L$ **and** $< 1.0 \times 10^9/L$ at baseline.
- Platelet response: increase from baseline of $\geq 30 \times 10^9/L$ **and** $< 100 \times 10^9/L$ at baseline.

Patients who met at least one of the 3 conditions of hematological response at any time between first day of treatment and week 24 will be considered as responders.

Analysis will be performed on FAS and PP set.

[figure not shown]
Further descriptive statistics on time to neutrophil and platelet improvement for patients who did not satisfied pre-treatment IWG criteria but show hematologic improvement according to modified IWG response criteria:

- Neutrophil improvement: increase from baseline $> 0.5 \times 10^9/L$
- Platelet improvement: increase from baseline of $\geq 30 \times 10^9/L$

will be provided along with summary on total time to hematological response ([Section 10.5.1](#)). Such analysis will be done for patients remaining in the EPO+DFX arm and EPO alone arm.

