To assess the effect of treatment with DFX+EPO and EPO alone on hematological response within 24 weeks of treatment	Proportion of patients achieving a hematological response within 24 weeks of treatment with DFX+EPO and EPO alone (increase in Hb, improvement of neutropenia and thrombocytopenia) according to modified IWG 2006 criteria	Refer to Section 10.5.1
To assess the effect of treatment on erythropoiesis within 24 weeks in patients that were non-responder to EPO alone within 12 weeks and switched to DFX+EPO	Proportion of patients achieving an erythroid response according to modified IWG 2006 criteria (increase in Hb \geq 1.5 g/dL) within 24 weeks in patients which were non-responder to EPO alone within 12 weeks and switched to DFX+EPO	Refer to Section 10.5.2
To assess the effect of treatment with EPO alone on erythropoiesis after 24 weeks of treatment	Proportion of patients achieving an erythroid response within 24 weeks of treatment with EPO alone (increase in Hb \geq 1.5 g/dL) according to modified IWG 2006 criteria	Refer to Section 10.5.4
To assess time to erythroid response in patients treated with DFX+EPO and patients treated with EPO alone	Time to erythroid response is defined as the time from date of start of treatment to the date of event defined as the first documented response according to modified IWG 2006 criteria (increase in Hb \geq 1.5 g/dL)	Refer to Section 10.5.3
To estimate time to erythroid response in patients who were non-responder to EPO alone after 12 weeks and switched to DFX+EPO	Time to erythroid response is defined as the time from date of switch (start of treatment with the combination) to the date of event , i.e. from week 13 to week 24, defined as the first documented response according to modified IWG 2006 criteria (increase in Hb \geq 1.5 g/dL)	Refer to Section 10.5.5
To estimate time to hematological response in patients treated with DFX+EPO and EPO alone within 24 weeks	Time to hematological response is defined as the time from date of start of treatment to the date of event defined as the first documented response (increase in Hb, improvement of neutropenia and thrombocytopenia) according to modified IWG 2006 criteria	Refer to Section 10.5.6

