4.1 Description of study design

This is an open-label, phase II, randomized, multi-center, pilot study to assess the efficacy in terms of erythroid improvement of DFX combined with EPO compared to EPO alone in patients with low- and int-1-risk MDS.

Patients will be randomly assigned to DFX plus EPO 40,000 units/week or to EPO 40,000 units/week alone in a 1:1 ratio. The dose of DFX DT will be 10 mg/kg/day and the dose of DFX FCT will be 7 mg/kg/day. At the time when DFX FCT study drug becomes available at a study site, all new patients who are randomized to combination therapy will receive the DFX FCT. Patients who are ongoing and receive DFX DT will continue with the DT. It is not permitted to change formulation during treatment. EPO dose changes after 4 and 12 weeks of study treatment will also be performed in both arms according to the EPO guidelines.

If after 4 weeks, increase in Hb is < 1 g/dL and total Hb is < 12 g/dL, the EPO dose will be increased to 60,000 units/week. If increase in Hb is ≥ 1 g/dL and total Hb is < 12 g/dL, patients will continue the current EPO dose. If Hb increase is ≥ 1 g/dL and total Hb is ≥ 12 g/dL, the patients will hold EPO treatment until end of study (Table 4-1).

If after 12 weeks of treatment with EPO alone, Hb increase is < 1 g/dL and total Hb is < 12 g/dL, the patient will switch to the combination therapy with EPO and DFX. If increase in Hb is ≥ 1 g/dL and total Hb is < 12 g/dL, patients will continue the current EPO dose. If Hb increase is ≥ 1 g/dL and total Hb is ≥ 12 g/dL, the patients will hold EPO treatment until end of study (Table 4-1).

[figure not shown]
If after 12 weeks of treatment with EPO in combination with DFX, Hb increase is < 1 g/dL and total Hb is < 12 g/dL, the patient will be discontinued from the study. If increase in Hb is ≥ 1 g/dL and total Hb is < 12 g/dL, patients will continue the current EPO dose plus DFX. If Hb increase is ≥ 1 g/dL and total Hb is ≥ 12 g/dL, the patients will hold EPO dose and receive treatment with DFX alone.

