1.1 Document content

[figure not shown]
This Report and Analysis Plan (RAP) module describes the planned statistical methods for all efficacy and safety analyses for phase II study CICL670A2421 which is an open-label, phase II, randomized, pilot study to assess the effect in term of erythroid improvement of deferasirox (DFX) combined with erythropoietin (EPO) compared to EPO alone in patients with low- and int-1-risk myelodysplastic syndrome (MDS).

It is structured as:

- A draft of Section 9.7 (Statistical methods planned in the protocol and determination of sample size)
- A draft of Appendix 16.1.7 and 16.1.9 (Documentation of statistical methods) of the CSR.

It is written in future tense. It will be reviewed and updated (including conversion to past tense) for entry into the clinical study report after the analysis has taken place.

The shells for the in-text tables and figures, post-text tables, figures and listings, and the table of contents will be in Module 7. Programming specifications, including derivations and imputation dates will be given in Module 8.

2 Clinical Study Report Section 9.7 - Statistical methods planned in the protocol and determination of sample size

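### Time to response is summarised in responders only, which mixes how many respond with how fast, and the SAP text contains no time-to-response or duration-of-response analysis

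*Protocol*

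**What the plan says.** Protocol 10.5.3 (time to erythroid response) sets the population first: "This analysis will include patients who were randomized to EPO and EPO+DFX and remained in their respective treatment arms". It then summarises days to response in those who responded: "Descriptive statistics will be provided for erythroid responder patients (achieved Hb increase ≥ 1.5 g/dL from baseline) for time to response (days". Protocol 10.5.6 (time to hematological response) has the same structure: "This analysis includes patients who started with combination therapy and EPO alone and remained in their respective treatment arms", followed by "Descriptive statistics will be provided for responder patients for time to response (days), defined as the time from date of start of treatment". Protocol 10.5.5 covers EPO patients who switched. It counts days from the switch, over weeks 13 to 24, again in responders only. None of the three sections gives a Kaplan-Meier or cumulative incidence estimate, or a censoring rule. All three name the FAS, which Protocol 10.1.1 defines as every randomised patient, analysed as assigned.

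Protocol Table 3-1 words the first of these objectives for treated patients, not for responders: "To assess time to erythroid response in patients treated with DFX+EPO and patients treated with EPO alone".

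SAP 1.1 states its scope: "This Report and Analysis Plan (RAP) module describes the planned statistical methods for all efficacy and safety analyses". Its secondary list runs from 2.9.2.1 to 2.9.2.5, and none of the five items is a time to response or a duration of response.

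Two wordings of the week-12 rule decide who remains in the EPO arm. Protocol 4.1 applies a threshold: "Hb increase is < 1 g/dL and total Hb is < 12 g/dL, the patient will switch to the combination therapy". Protocol 10.5.2 and SAP 2.9.2.2 instead move every erythroid non-responder on EPO who continues in the study to the combination.

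**The concern.** Whether a patient enters the summary depends on the outcome. Non-responders and the time they spent at risk are left out, so the mean or median describes a different, self-selected group in each arm. If a treatment brings in extra responders, the statistic moves according to when those patients respond, even if nobody else responds sooner or later than before. Two columns of responder days placed side by side can then be read as a difference in speed that no patient experienced.

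The restriction to patients who stayed in their arm adds a second outcome-dependent filter, because EPO patients leave their arm through a poor hemoglobin response at week 12.

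The SAP raises a separate issue. Five secondary objectives have no analysis in its text, and no reason is given. A reader cannot tell whether the protocol's summaries will be produced.

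**Working it through.** **1. Inputs.** Protocol: 60 patients, 1:1, so 30 per arm; reference response 40% with a 20-point gain as one scenario (10.8). That is 12 of 30 against 18 of 30. Nominal hemoglobin days from SAP Table 4-1: Visits 5, 7, 9, 10, 11 and 12 at Days 14, 28, 56, 84, 112 and 140. The documents give no distribution of response times and no figure for this endpoint, so there is nothing to reproduce. All timings below are assumptions.

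**2. Base example.**
- EPO: 6, 4 and 2 responders at Days 28, 56 and 84. Mean = (6×28 + 4×56 + 2×84)/12 = 560/12 = 46.7 days. Median = (28 + 56)/2 = 42.
- Combination: the same 12 plus six at Day 84. Mean = (560 + 6×84)/18 = 1064/18 = 59.1 days. Median = 56.
- Cumulative response over all 30 at Days 28/56/84: 20/33/40% against 20/33/60%.

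The responder summary is 12.4 days (mean) or 14 days (median) longer on the combination, yet that arm is never behind.

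**3. Range over timing.** Add Day 14 and take the EPO reference as 2, 4, 4 and 2 responders at Days 14, 28, 56 and 84. Mean = 532/12 = 44.3.

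| Combination arm | Responders | Median | Mean | Cumulative % at Days 14/28/56/84 |
|---|---|---|---|---|
| Same as EPO reference | 12 | 42 | 44.3 | 7/20/33/40 |
| +6 at Day 84 | 18 | 56 | 57.6 | 7/20/33/60 |
| +9 at Day 84 | 21 | 84 | 61.3 | 7/20/33/70 |
| +3 at Day 56, +3 at Day 84 | 18 | 56 | 52.9 | 7/20/43/60 |
| +3 at Day 112, +3 at Day 140 | 18 | 56 | 71.6 | 7/20/33/40 (60 by Day 140) |
| +6 in proportion | 18 | 42 | 44.3 | 10/30/50/60 |
| +6 at Day 28 | 18 | 28 | 38.9 | 7/40/53/60 |

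No row has lower cumulative response than the reference at any visit, but the responder mean runs from 38.9 to 71.6 days. Over five different reference timings, six responders added at Day 84 raised the mean by 4 to 16 days each time. In the second row the difference in means is 13.2 days, with a 95% CI of about -5.6 to 32.0.

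**4. The stayed-in-arm restriction.** Give both arms the same response process: the 12 reference responders by week 12, plus three late ones (two at Day 112, one at Day 140) whose rise at week 12 was 1 to under 1.5 g/dL.
- Under the 10.5.2 wording these three leave the EPO arm. EPO then has median 42 and mean 44.3. The combination keeps them: median 56, mean (532 + 2×112 + 140)/15 = 896/15 = 59.7. The gap comes from the restriction alone.
- Under the 4.1 wording they stay in both arms, and this asymmetry does not arise.

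**5. Protocol against SAP.** SAP 2.9.2.1 to 2.9.2.5 correspond to Protocol 10.5.1, 10.5.2, 10.5.4, 10.5.9 and 10.5.10. Unmatched are 10.5.3, 10.5.5 and 10.5.6 (time to response) and 10.5.7 and 10.5.8 (duration). All five are in Table 3-1.

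**The case against.** The protocol labels these summaries openly as responder statistics and promises no difference, interval or test between arms. Section 10.5.5 concerns a single group. Days to response among responders and the proportion responding are different quantities, so one cannot strictly contradict the other. The study is a pilot without formal sample sizing. Added responses are already measured by the primary endpoint and by the 12- and 24-week hematological response in SAP 2.9.2.1, and the hemoglobin time course by visit (SAP 2.9.2.5) gives a view of speed. All of this stands. It rules out calling time to response the only secondary objective able to show a benefit of DFX.

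A reader might also infer that the report will show DFX delaying response by about two weeks. The documents do not support that: it requires late extra responders, and early ones reverse the direction.

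Nor can the misleading summary and the missing analysis both occur. If the SAP text is complete and governs, no responder mean is produced.

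Finally, the omission may be explained elsewhere. The SAP's list of tables cites a document history that is not in the public text, Modules 7 and 8 are separate, and SAP 2.1 points generally to protocol section 10. That pointer supplies no method, so the claim is limited to absence from the available text.

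What remains is that the statistic does not answer an objective stated for treated patients, and that the two documents disagree on whether it will be calculated.

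**Conclusion.** The point holds in limited form. Time to response under Protocol 10.5.3, 10.5.5 and 10.5.6 is conditional on responding, and in 10.5.3 and 10.5.6 also on staying in the arm, so it cannot separate speed from number of responses. In the base example this shifts the mean by 12.4 days and the median by 14 with no patient slower. Both size and direction rest on assumed timings, and with 12 and 18 responders the difference is imprecise. Separately, time to response and duration of response are absent from the public SAP text although they are secondary objectives. Either they go unreported or a summary open to misreading is used; the documents do not settle which. The primary week-12 comparison is not affected. This is a worthwhile, inexpensive improvement to descriptive secondary analyses, not a threat to the trial's main result.

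**What to change.** In SAP 2.9.2:

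1. Reinstate time to erythroid and time to hematological response, or state that they are omitted and why. Say the same explicitly for the two duration analyses.
2. Estimate cumulative incidence by randomised arm in all FAS patients. Either start the clock at randomisation, or start at first dose and count untreated patients as non-responders, since the FAS includes them (SAP Table 4-7, S01).
3. Treat withdrawal before response as a competing event, and censor only at administrative end of follow-up. Censoring non-responders at their last hemoglobin would be informative, because Protocol 7.1.3.1 requires withdrawal when rescue transfusion is needed.
4. Report the proportion responding by Visits 5, 7, 9 and 10 with 95% CI, as the randomised comparison before the planned switch.
5. Show weeks 13 to 24 as a descriptive extension with a stated rule for switch and discontinuation. First reconcile the switch wording in Protocol 4.1 with that in 10.5.2 and SAP 2.9.2.2.
6. Give switchers a single curve from first DFX dose. Keep responder-only days as a labelled supplementary summary.

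The cost is SAP text, one table and one figure, from hemoglobin and count data already collected.
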